# Specific Aims:

(1) Compare the effectiveness of intradermally-injected autologous platelet-rich plasma versus normal saline to improve burn scars, as measured by both clinician-reported (Vancouver scar scale; VSS) and patient-reported measures (Patient and Observer Scar Assessment Scale; POSAS).

(2) Compare the effectiveness of intradermally-injected autologous platelet-rich plasma versus normal saline as a control to improve neuropathic pain associated with burn scars.

(3) Understand the mechanism of action of PRP in improving burn scars via histological analysis of collagen content in the burn scar tissue biopsy specimens.

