# 4. Inclusion/Exclusion Criteria

Inclusion Criteria:

- 18-70 years old, all sexes
- Thermal burn scar on the trunk or abdomen ≥ 1 year old that meets ONE of the following criteria:
  - Vancouver Scar Scale score  $\geq 7$
  - Patient and Observer Scar Assessment Scale (POSAS) score ≥ 35
  - Neuropathic symptoms
    - POSAS score ≥ 5 on question evaluating itchiness
    - POSAS score  $\geq$  5 on question evaluating pain

Exclusion Criteria:

- Initial burn injury was less than 1 year old
- History of chemical or electrical burn
- History of CO2 treatment to the scar of interest
- Genetic or acquired conditions that severely affect systemic wound healing or collagen formation (vasculitis, diabetes, Ehlers-Danlos syndrome, radiation therapy to the scar site or use of immunosuppressive medications within the last year, active cancer)

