# 5. Enrollment/Randomization

Prior to enrollment, all sixty potential study ID numbers will be randomly assigned to a treatment group (Right/Left). The randomization will be performed by coin flip (heads is right, tails is left). This will be logged in a secure REDCAP form only accessible by the researcher not conducting scar evaluations (unblinded REDCAP). There will be a secondary REDCAP form used for logging VSS/POSAS scores that does not contain this information (blinded REDCAP).

Potential candidates will be identified by the attending surgeon at the Burn Reconstruction Clinic at Vanderbilt. All patients meeting preliminary inclusion/exclusion criteria will be contacted, via phone or in person at the clinic, and given a brief description of the study. If interested in participating, inclusion/exclusion criteria will be reviewed with the patient, and the patient will be scheduled for their first appointment. Patients will be assigned to a study ID number (with associated treatment group) based on order of enrollment.

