## 6. Study Procedures

# Day 1:

When the patient first arrives, they will be given a copy of the patient POSAS, the study information sheet, and the demographics sheet to review and fill out while in the waiting room. The demographics sheet will collect the following demographic information: MRN, date of birth, sex, %TBSA, comorbidities (diabetes, smoking, hypertension, history of radiation or chemotherapy, history of cancer), presence of skin graft and type (xeno- or allograft) and location, size and donor site of skin graft used, race, Fitzpatrick skin type, mechanism of injury (e.g., flame, scald, radiator, etc.), current medications (in particular, any anti-inflammatories, anti-neoplastics, or steroids), and prior scar treatments, including over the counter creams or lotions.

Once roomed, a provider will administer both the VSS and the observer POSAS to confirm that the patient meets inclusion criteria. A secondary provider will also administer a VSS and POSAS.

After determining that the patient meets inclusion criteria, the consent form will be reviewed in depth to describe the purpose and procedures associated with the study. The consent form, demographics form, and VSS/POSAS scores will be logged into the blinded REDCAP.

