For the procedure itself, 6mL of anticoagulant citrate dextrose A (ACD-A) will be drawn up in a 60mL syringe, after which 44 mL of the patient's own venous blood will be drawn into the same 60mL syringe using standard venipuncture techniques (Bellus Medical, 2019). While patient is waiting in the examination room, the sterile tubes of blood will be centrifuged by the ELMI CM-7S centrifuge which takes approximately 10-15 minutes. While waiting for the PRP to undergo centrifugation the scar to be treated will first be wiped with an alcohol swab, then measured and marked out with a marking pen such that the entirety of the scar will fit into a rectangle that is drawn, and the rectangle is filled entirely with the scar tissue. A ruler will be used to measure the scar in its greatest horizontal span, and the midway point will be marked with a vertical line. The length and height of the rectangle will be recorded. The vertical and horizontal distance from the nearest point-like anatomic landmark (e.g., xiphoid process) to the two edges of the rectangle will be documented so that the rectangle can be recreated at a later date. A photo of the outlined scar(s) will be obtained with a digital camera, with a ruler in view placed against the skin adjacent to the scar for reference as well as a "L" and "R" to designate laterality. The area inside the rectangle will then be subdivided with a marking pen into 1cm x 1cm square boxes, with the plan of injecting 1mL of either PRP or normal saline into each 1 square cm box.

The unblinded researcher who does not participate in the scar assessments will review the unblinded REDCAP containing the pre-designated treatment group (termed "Right and Left") and will inject the PRP and saline into the scar. The syringes will be covered with a white sticker and labeled such that the patient is unable to infer which syringe contains PRP (PRP is yellow

with a red hue and normal saline is clear). The unblinded researcher will then log this treatment into the unblinded REDCAP.

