#### **10. Statistical Considerations**

-Our proposed study is methodically similar to "Treatment of traumatic scars using fat grafts mixed with platelet-rich plasma and resurfacing of skin with the 1540 nm non-ablative laser" by Cervelli et al., and we expect to analyze a similar population and outcome. In this study, they

met power with 31 patients. We will plan to enroll 35 patients, but we will recruit 40 with an expected 10% attrition.

-In our study, data will be recorded in a spreadsheet (Excel; Microsoft Corp., Redmond, WA, USA) and analyzed with SPSS software for Windows (version 15.0; SPSS, Chicago, IL, USA). Descriptive statistics will include mean ± SD for parametric variables, and median and range for nonparametric variables. The median will be used to test the difference between the groups before and after treatment, and the Wilcoxon signed rank test will be used to examine differences within groups before and after treatment. P<0.05 will be considered significant.

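### One unadjusted P<0.05 rule covers unranked outcomes and several visits with no primary comparison, so the overall chance of a false positive exceeds 5%

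*Combined protocol and SAP*

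**What the plan says.** Section 10 sets one threshold, "P<0.05 will be considered significant", and attaches it to no outcome and no visit. For the comparison of PRP with saline it says only "The median will be used to test the difference between the groups before and after treatment", without naming a test. The one named test, the Wilcoxon signed rank test, is for change within each group.

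Aim 1 judges scar improvement "as measured by both clinician-reported (Vancouver scar scale; VSS) and patient-reported measures", the second being POSAS. Aim 2 compares PRP with "normal saline as a control to improve neuropathic pain associated with burn scars". The only pain score described is a POSAS item, which appears in the Section 4 eligibility criteria as a score of at least 5 "on question evaluating pain". Aim 3 is histological. The aims are numbered, but nothing says the numbers are a testing order.

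In Section 6, VSS and POSAS are completed at month 1, and months 2, 3 and 4 repeat that visit. At months 1 to 4 the scoring comes before that visit's injections. The scales are completed again at month 5 and, because one heading covers both visits, apparently at one year.

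On Day 1, "Once roomed, a provider will administer both the VSS and the observer POSAS to confirm that the patient meets inclusion criteria". Only later in that section is the scar measured across, after which "the midway point will be marked with a vertical line". No supplied text says that scores are recorded for each half.

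**The concern.** A 5% threshold limits the false-positive risk to 5% only when a single prespecified test decides the question. Here at least two scales serve Aim 1 and a third outcome serves Aim 2, each eligible for the same unadjusted threshold. The visit that counts as after treatment is also open.

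If PRP does nothing, the chance that something reaches P<0.05 is therefore above 5%. A claim of effectiveness could then rest on whichever scale or visit was significant, and a reader could not tell from the plan whether that comparison had been chosen in advance.

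**Working it through.** **Inputs from the documents.** Threshold 0.05 per test (Section 10; sidedness is not stated, so two-sided is assumed). Outcomes: VSS, POSAS and pain (Aims 1 and 2). Follow-up scoring visits: months 1 to 5 and, by implication, one year (Section 6), so up to six. Planned sample: 35 patients (Section 10).

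**Assumed, because the documents are silent.** One paired PRP-versus-saline test per outcome and visit; correlations between outcomes of 0.3, 0.5, 0.6 or 0.8, paired with correlations between visits of 0.5, 0.7, 0.8 or 0.9.

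**Step 1: the plan's own figure.** For one test, 1 − (1 − 0.05) = 0.05. The stated level is exact for a single test.

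**Step 2: two tests.** If independent, 1 − 0.95² = 0.0975. With correlation 0.95 the simulated value is 0.064. Any two 5% tests that are not perfectly dependent exceed 5% together, so the direction does not depend on the assumed correlations.

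**Step 3: correlated tests under no effect.** Simulated z-tests, 400,000 replicates per setting. Each cell gives the chance of any P<0.05, then the chance of at least one significant result favouring PRP. Columns show visit correlation / outcome correlation.

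| Tests | 0.5 / 0.3 | 0.7 / 0.5 | 0.8 / 0.6 | 0.9 / 0.8 |
|---|---|---|---|---|
| One outcome, one visit | 0.050; 0.025 | 0.050; 0.025 | 0.050; 0.025 | 0.050; 0.025 |
| VSS, POSAS; one visit | 0.095; 0.048 | 0.090; 0.045 | 0.088; 0.044 | 0.077; 0.039 |
| Plus pain; one visit | 0.137; 0.069 | 0.125; 0.063 | 0.118; 0.059 | 0.098; 0.049 |
| Three outcomes; month 5 and year 1 | 0.238; 0.120 | 0.203; 0.101 | 0.179; 0.090 | 0.134; 0.067 |
| Three outcomes; months 1–5 | 0.436; 0.228 | 0.340; 0.171 | 0.279; 0.139 | 0.189; 0.094 |
| Three outcomes; all six visits | 0.484; 0.255 | 0.370; 0.188 | 0.301; 0.150 | 0.201; 0.100 |

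The last two rows describe testing that the plan permits but does not state.

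**Step 4: check with signed-rank tests.** With 35 pairs and 6,000 simulated trials, the chance of any P<0.05 at the first and last correlation settings was 0.098 and 0.082 (two outcomes, one visit), 0.133 and 0.096 (three outcomes, one visit), and 0.238 and 0.141 (three outcomes, two visits). These agree with the table.

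**Step 5: candidate remedies.** These treat patient POSAS and observer POSAS separately, giving four outcomes at one visit. Columns show outcome correlation.

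| Rule | 0.3 | 0.5 | 0.6 | 0.8 |
|---|---|---|---|---|
| Unadjusted | 0.174 | 0.155 | 0.144 | 0.114 |
| VSS first, then Holm on the other three | 0.050 | 0.050 | 0.050 | 0.050 |
| One Holm set of four | 0.047 | 0.042 | 0.040 | 0.032 |
| VSS at 0.05 plus a separate Holm family of three | 0.092 | 0.084 | 0.080 | 0.066 |

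If VSS has a real effect detected with 80% power and the other three have none, the VSS-first rule gives a false positive among those three with probability 0.018–0.035.

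**Step 6: detectable difference at n = 35, 80% power.** In SDs of the paired difference, (z[1 − α/2] + z[0.80]) / √35:
- α = 0.05: (1.960 + 0.842) / 5.916 = 0.474
- α = 0.05/3: (2.394 + 0.842) / 5.916 = 0.547
- α = 0.05/4: (2.498 + 0.842) / 5.916 = 0.564

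Paired t-tests give 0.49, 0.57 and 0.59.

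**The case against.** **Both scales may be required.** Section 10 does not say that any one significant outcome counts as success, and Aim 1 refers to both kinds of measure. If VSS and POSAS both had to be significant, the null error would be 0.05 + 0.05 − 0.095 = 0.005 at correlation 0.3 and 0.05 + 0.05 − 0.077 = 0.023 at 0.8, below 5%. That would be a legitimate rule, but Section 10 does not state it. It would not cover Aim 2, and it does not change the chance that at least one of the tests is falsely significant.

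**The modelled test is not the named test.** This is fair. Section 10 names a test only for change within groups, so the between-side test is an assumption. The statement that about half the errors favour PRP depends on it. The within-group tests are left out of the count.

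**The visit count may be too generous.** Injections are described through month 4, so after treatment may well mean month 5, one year or both. This stands: the five- and six-visit rows should not be quoted as the expected effect. Nor are they upper bounds, since splitting POSAS gives 23–58% over six visits. The one- and two-visit rows do not depend on this point.

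**Scoring by half is a separate matter.** Within-group change over time does imply scores for each half. However, no procedure records them that way, and the proposed comparison cannot be calculated without them at follow-up.

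**Text not supplied.** Two parts of the document were withheld from review. From their position they appear to be front matter and adverse-event text. The finding is limited to what was supplied.

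**Conclusion.** The concern holds. As written, the plan does not control the overall false-positive rate. That rate exceeds 5% as soon as the two Aim 1 scales are each tested once: 8–10% for those two, 10–14% with pain, and 13–24% for the three outcomes at month 5 and one year, against 5% for a single test. Errors favouring PRP are 4–5%, 5–7% and 7–12% respectively, against 2.5%.

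The direction needs only that two or more imperfectly dependent tests are each judged at 0.05. The sizes rest on the assumed correlations and on one paired between-side test per outcome. The plan should be changed before analysis; the design itself need not change.

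**What to change.** **Section 10.** State one primary between-side comparison at one visit, at two-sided 0.05. An example is the within-patient PRP-minus-saline difference in VSS change from Day 1 to month 5, using the mean of the blinded raters' scores. Month 5 is the first visit after the last described injection. Only if this is significant, test patient POSAS, observer POSAS and the POSAS pain item at the same visit by Holm at 0.05. If Aim 2 must be able to succeed when VSS fails, put all four in one Holm set instead. Either rule holds the overall error at 5% or less. A separate Holm family for the three secondaries leaves 7–9%, which must be stated if chosen. Report other visits, items and histology as estimates with 95% confidence intervals and no significance claims. The sponsor may prefer another outcome or visit, provided it is fixed before analysis.

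**Section 6.** Confirm that VSS and POSAS are recorded for each half at Day 1 and at follow-up. If no Day 1 score by half exists, compare the halves directly at the chosen visit. A whole-scar baseline cancels from the paired difference, and the treated side is randomised: "The randomization will be performed by coin flip (heads is right, tails is left").

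**Cost.** A few sentences in Section 10, one in Section 6, and possibly completing existing forms for each half. Fewer outcomes can support a significance claim; under the VSS-first order, pain cannot if VSS fails. At 35 patients the difference detectable with 80% power is 0.47 SD for the primary, 0.55 SD at the first Holm step for three secondaries and 0.56 SD at the first step of a Holm set of four. These are normal approximations; a signed-rank test at 0.474 SD has about 75% power. Without a Day 1 score by half, the SD of the comparison is 1/√(2(1 − ρ)) times that of the change comparison, assuming equal variances. Here ρ is the assumed correlation of the side difference between Day 1 and month 5: 0.85 at ρ = 0.3, 1.00 at 0.5 and 1.29 at 0.7.

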# 11. Privacy/Confidentiality Issues

Private health information (PHI) will used in the study, but not disclosed. All PHI will be stored on a secure, password-locked server. All participants in the study have obtained Human Research certification to have the necessary authorization to PHI. When collecting patient data, only medical record numbers will be used to identify patients.

# 12. Follow-up and Record Retention

The study will last for approximately 1 year after initiation. At the study conclusion, all identifiable data will be destroyed, and de-identified data will be kept for analysis.
